¹³ The investigator and subject will assess each Target Wart for local skin reactions associated with irritation at Visits 2-13. At Visit 2-Visit 9, the investigator and subject will assess the Target and Non-Target Warts for LSRs prior to the application of the study medication. The subject will assess LSRs 10 (\pm 4) minutes after the application of A-101 study medication and the investigator will assess for LSRs 20 (\pm 4) minutes after application of A-101 study medication. Refer to Section 9.1 for the complete list of Local Skin Reaction signs and symptoms.

¹⁴The investigator will apply the A-101 study medication to subject 8 to 17 years of age. Subjects 18 years of age and older will apply their A-101 study medication in the presence of the treating physician or a member of the investigational study staff that has been trained on the protocol. All Target and Non-Target Warts will be treated with study medication following randomization at Visit 2. If a Target or Non-Target Wart meets the criteria for re-treatment as defined in Section 7.6 the lesion will be re-treated at Visit 3-9. Following application of study medication, subjects must NOT wash/submerge the Target or Non-Target Warts for at least 6 hours and they must NOT apply any topical products to the Target or Non-Target Warts for at least 6 hours.

Page 22 of 53 Amendment 2 Version 3 Date: 05 December 2017 ¹⁵Sites will be required to weigh all A-101 study medication applicators before and after treatment and document the weight of each applicator in the subject's eCRF.

¹⁶All concomitant therapies including (topical and oral) prescription medications, over the counter medications and natural supplements and non-drug therapies including chiropractic, physical therapy, and energy based therapy must be documented in the subject CRF. Subjects must not apply any topical products (e.g., moisturizers, sunscreen, etc.) to their Target or Non-Target Warts within 12 hours prior to any study visit.

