6.1. Local Skin Reactions (LSR)

The LSR assessment is the Investigator's assessment of the signs and the subject's assessment of the symptoms associated with irritation at the Target/Non-Target Wart site (*i.e.*, the Target/Non-Target Wart and the skin immediately surrounding the Target/Non-Target Wart exposed to study medication). The Investigator may refer to previous photographs to assist with these assessments only after the PWA has been performed.

The Local Skin Reaction signs to be assessed are:

- Erythema
- Edema
- Erosion
- Ulceration
- Vesicles/bullae
- Excoriations
- Scabbing.

The Local Skin Reaction symptoms to be assessed (by the Subject) are:

- Stinging/burning
- Pruritus (itch).

At Visits 2-13, the Investigator will evaluate the LSR signs at the Target/Non-Target Wart site(s) as follows:

- At visits where a study medication treatment or retreatment is performed:
 - Perform an LSR assessment prior to any study medication application
 - For treated Target and Non-Target Warts perform an LSR assessment 20 (±4) minutes after the Treatment Completion Time.

At Visits 2-13, the Subject will assess the LSR symptoms at the Target/Non-Target Wart site(s) as follows:

- At visits where a study medication treatment or retreatment is performed:
 - Perform an LSR assessment prior to any study medication application
 - For every treated Target and Non-Target Wart site, 10 (±4) minutes after the Treatment Completion Time, report the average of the severity of the LSR for all symptoms since completion of the study medication treatment.
- At visits where no study medication treatment is performed: • Perform an LSR assessment.

The Investigator and subject should report the one integer that best describes the severity of each LSR sign or LSR symptom for the Target and Non-Target Wart sites using the scale below.

	Local Skin Reactions	
Grade	Descriptor	
0	None	
1	Mild	
2	Moderate	
3	Severe	

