7.5. Treatment Compliance

Study medication use and accountability will be presented in a listing. Overall study medication use will be summarized by treatment group.

8. **PRESENTATIONS OF SAFETY INFORMATION**

Descriptive statistics by treatment group will be calculated on the safety parameters collected on or after Visit 3 using the Safety Population, defined as subjects who received at least one application of study medication. Safety summaries will include listings of clinical laboratory values and abnormal values, adverse events incidences within each Medical Dictionary for Regulatory Activities (MedDRA) System Organ Class, and changes from pre-dose values in vital signs. Adverse event summaries will be presented showing the proportion of patients experiencing adverse events, both overall and by MedDRA System Organ Class.

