8.5. Local Skin Reactions

Local Skin Reaction (LSR) scores will be summarized by frequency distributions for each symptom, by treatment group and visit. The proportion of subjects with with Severity > 0, and similarly for subjects with Severity > 1 will be presented for each symptom, by visit.

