SAFETY DATA SUMMARY TABLES

Displays of Study Medication Exposure and Adverse Events

- Table 14.3.1
 Study Medication Treatment Summary Safety Population
- Table 14.3.1.1
 Summary of Treatment-Emergent Adverse Events Safety Population
- Table 14.3.1.2
 Treatment-Emergent Adverse Events by System Organ Class Safety

 Population
- Table 14.3.1.3Treatment-Emergent Adverse Events in Decreasing Order of Frequency by
Preferred Term Safety Population
- Table 14.3.1.4Treatment-Emergent Adverse Events by Maximum Intensity, System OrganClass and Preferred Term Safety Population
- Table 14.3.1.5Treatment-Emergent Adverse Events Considered Treatment Related by
System Organ Class Safety Population
- Table 14.3.1.6Subjects Who Discontinued Study Drug Due to Adverse Events by System
Organ Class

Listings of Deaths, Other Serious and Significant Adverse Events

Table 14.3.2.1	Treatment-Emergent Serious Adverse Events by System Organ Class -
	Safety Population
Table 14.3.2.2	Treatment-Emergent Serious Adverse Events in Decreasing Order of
	Frequency by Preferred Term – Safety Population
Table 14.3.2.3	Treatment-Emergent Serious Adverse Events Considered Treatment Related
	by System Organ Class – Safety Population

Abnormal Laboratory Value Listing

Table 14.3.4.1	Lab Results	Outside Normal	Range,	Battery	Name:	Chemistry
----------------	-------------	----------------	--------	---------	-------	-----------

Table 14.3.4.2Lab Results Outside Normal Range, Battery Name: Hematology

Other Safety Data

- Table 14.3.5.1Treated Wart Local Skin Reactions (Evaluated by Subject), Frequency
Distribution by Symptom, Treatment and Visit
- Table 14.3.5.2Treated Wart Local Skin Reactions (Evaluated by Investigator), Frequency
Distribution by Symptom, Treatment and Visit
- Table 14.3.5.3Treated Wart Local Skin Reactions (Evaluated by Subject), Number and %
of Subjects for Each Symptom and Visit, With Target Wart Severity > 0
(None)

Table 14.3.5.4	Treated Wart Local Skin Reactions (Evaluated by Investigator), Number and % of Subjects for Each Symptom and Visit, With Target Wart Severity > 0 (None)
Table 14.3.5.5	Treated Wart Local Skin Reactions (Evaluated by Subject), Number and % of Subjects for Each Symptom and Visit, With Target Wart Severity > 1 (Mild)
Table 14.3.5.6	Treated Wart Local Skin Reactions (Evaluated by Investigator), Number and % of Subjects for Each Symptom and Visit, With Target Wart Severity > 1 (Mild)

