Table 14.3.5.7	Mean and Mean Change from Pre-Treatment in Vital Signs: Systolic Blood Pressure (mm Hg)
Table 14.3.5.8	Mean and Mean Change from Pre-Treatment in Vital signs: Diastolic Blood Pressure (mm Hg)
Table 14.3.5.9	Mean and Mean Change from Pre-Treatment in Vital signs: Pulse Rate (beats/min)
Table 14.3.5.10	Mean and Mean Change from Pre-Treatment in Vital signs: Respiratory Rate (breaths/min)
Table 14.3.5.11	Mean and Mean Change from Pre-Treatment in Vital signs: Body Temperature (deg F)
Table 14.3.5.12	Concomitant Medications – Safety Population

SUBJECT DATA LISTINGS

16.2.1	Discontinued Subjects
Listing 16.2.1.1	Disposition of Subjects
16.2.2	Protocol Deviations
Listing 16.2.2.1	Protocol Deviations/Violations
16.2.4	Demographic Data
Listing 16.2.4.1	Demographic Information and Informed Consent
Listing 16.2.4.2	Medical History and Concomitant Conditions
Listing 16.2.4.3	Prior and Concomitant Medications
16.2.5	Compliance Data [See L6,7,7.1]
Listing 16.2.5.1	Study Medication Inventory
Listing 16.2.5.2	Randomization and Study Medication Application
16.2.6	Efficacy Data
Listing 16.2.6.1	Treated Wart Assessments: PWA Values by Treatment and Visit
Listing 16.2.6.2	Treated Wart Assessments: PWA responders with PWA Clear ($PLA = 0$)
	at Visit 10, by Treatment and Visit
Listing 16.2.6.4	Treated Wart Assessments: PWA Responders with PWA <= 1 at Visit 10, by Treatment and Visit
Listing 16.2.6.5	Treated Wart Dimensions – Length of Longest Axis, Values by
	Treatment
16.2.7	Adverse Event Listings
Listing 16.2.7.1	Mapping of MedDRA System Organ Class, MedDRA Preferred Term, and CRF Verbatim Terms
Listing 16.2.7.2	Treatment Emergent Adverse Events
Listing 16.2.7.2.1	Treatment Emergent Serious Adverse Events
Listing 16.2.7.3	Treatment Emergent Adverse Events Classified as Cutaneous by Investigator
16.2.8	Laboratory Listings
Listing 16.2.8.1	Female Pregnancy Tests
Listing 16.2.8.2	Lab Battery Name: Chemistry
Listing 16.2.8.3	Lab Battery Name: Chemistry: Results Outside Normal Range
Listing 16.2.8.4	Lab Battery Name: Hematology & Differentials
Listing 16.2.8.5	Lab Battery Name: Hematology & Differentials: Results Outside Normal Range

Page 31 of 32 Date: 21 November 2017

16.2.9	Other Listings
Listing 16.2.9.1	Treated Wart Local Skin Reactions (Evaluated by Subject), Values by
	Symptom, Treatment, and Visit
Listing 16.2.9.2	Treated Wart Local Skin Reactions (Evaluated by Investigator), Values
	by Symptom, Treatment and Visit
Listing 16.2.9.3	Vital Signs

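### The skin-reaction tables count any grade above 0 or above 1 without reference to the Visit 2 pre-application grade, so irritation present before the first dose that persists is counted as a reaction

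*SAP*

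**What the plan says.** SAP Section 8.5 plans two LSR displays. The first is descriptive: "Local Skin Reaction (LSR) scores will be summarized by frequency distributions for each symptom, by treatment group and visit". The second is the proportion of subjects with "Severity > 0, and similarly for subjects with Severity > 1 will be presented for each symptom, by visit". Tables 14.3.5.3 to 14.3.5.6 in SAP Section 11 carry out the second. They give subject-rated and investigator-rated results, at each cut, as the number and percentage "of Subjects for Each Symptom and Visit, With Target Wart Severity > 0" or above 1. No treatment-emergent, shift or change-from-baseline definition for LSRs appears in the protocol or the SAP.

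A baseline grade is collected. For treatment visits, SAP Section 6.1 says: "Perform an LSR assessment prior to any study medication application". Footnote 13 to the schedule in Protocol Section 6 says that at Visits 2 to 9 "the investigator and subject will assess the Target and Non-Target Warts for LSRs prior to the application of the study medication". The Visit 2 value is therefore a grade before any exposure, recorded for each wart.

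SAP Section 8 sets the data window: "Descriptive statistics by treatment group will be calculated on the safety parameters collected on or after Visit 3". Other safety measures do use a reference. Vital signs have tables titled "Mean and Mean Change from Pre-Treatment in Vital Signs", and adverse events are summarised as treatment-emergent (SAP Section 8.1).

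**The concern.** Several of the graded items, such as erythema, excoriations, scabbing and itch, are not specific to the study drug. Protocol Section 2.1 notes that warts are common at sites prone to trauma. The exclusions for sunburn, open wounds and current skin disease depend on the investigator's judgement of risk or interference, so they reduce irritation at entry without ruling it out.

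Under an absolute cut, a subject who is grade 1 before the first application and still grade 1 at a later visit is counted in the same way as a subject whose skin reacted to the product. Because the safety window starts at Visit 3, the reader would not necessarily see the pre-dose level beside the later rates. The group-level baseline summary in SAP Section 7.4 might show the prevalence, but it cannot show which later positives were already positive.

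The LSR tables carry much of the local tolerability evidence. If background signs exist, the rates in both arms are too high as measures of reaction, and the A-101 to vehicle ratio is pulled toward 1.

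**Working it through.** **Plan's own figure.** There is none to reproduce. The documents give no LSR rate by arm and no prevalence of signs before dosing. Protocol Section 2.2 says only that reactions in the previous study were generally transient. All rates below are assumptions.

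**Inputs.**
- p0: share of subjects above the cut for a given sign before the first application and still above it later. Assumed 5, 15 and 25%, the same in both arms.
- qA, qV: study-induced reaction rates, assumed 60% on A-101 and 10% on vehicle, independent of baseline status.
- w: among subjects already positive at Visit 2, the share of induced reactions that exceed the subject's own Visit 2 grade. Unknown, between 0 and 1.

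**Planned rule (absolute cut).** Rate = p0 + (1 − p0) × q, so the difference is (1 − p0) × (qA − qV). For p0 = 5%: A-101 is 0.05 + 0.95 × 0.60 = 62%, and vehicle is 0.05 + 0.95 × 0.10 = 14.5%.

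**Baseline-referenced rule (grade above own Visit 2 grade, all subjects in the denominator).** Rate = (1 − p0) × q + p0 × w × q. With w = 0 and p0 = 5%: 0.95 × 0.60 = 57% and 0.95 × 0.10 = 9.5%.

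| p0 | Planned rule, A-101 / vehicle | Difference | Ratio | Baseline-referenced, w = 0 | Difference | Ratio |
|---|---|---|---|---|---|---|
| 0% | 60 / 10% | 50 points | 6.00 | 60 / 10% | 50 points | 6.00 |
| 5% | 62 / 14.5% | 47.5 | 4.28 | 57 / 9.5% | 47.5 | 6.00 |
| 15% | 66 / 23.5% | 42.5 | 2.81 | 51 / 8.5% | 42.5 | 6.00 |
| 25% | 70 / 32.5% | 37.5 | 2.15 | 45 / 7.5% | 37.5 | 6.00 |

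The overstatement in each arm is p0 × (1 − q). That is 4.5, 13.5 and 22.5 points on vehicle, and 2, 6 and 10 points on A-101.

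**Effect of w.** At p0 = 25% and w = 0.5, the baseline-referenced rates are 0.45 + 0.25 × 0.5 × 0.60 = 52.5% and 0.075 + 0.25 × 0.5 × 0.10 = 8.75%, a difference of 43.75 points. At w = 1 they are 60% and 10%, and the full 50 points return. The ratio is 6.00 at every w.

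**Other assumed rates.** With p0 = 20% and an induced ratio of 3.00, the planned rule gives:
- 30/10% induced: 44/28%, ratio 1.57
- 60/20% induced: 68/36%, ratio 1.89
- 90/30% induced: 92/44%, ratio 2.09

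**Chance imbalance.** With about 60 subjects per arm and p0 = 15%, the 95% range of the between-arm difference in baseline prevalence is ±1.96 × √(2 × 0.15 × 0.85 / 60) = ±0.128, about 13 points either way. Under the planned rule, baseline imbalance that persists passes into the later rates.

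**The case against.** There is a good case against reading much into this.

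- **Conditional on unknowns.** Inflation needs signs that exist at Visit 2 and persist, and the documents give neither prevalence nor persistence. The periods required since earlier wart treatments are washouts that reduce residual irritation, and the skin-condition exclusions remove more. This stands.
- **One p0 for every table is crude.** The tables run by sign or symptom, by visit and at two cuts. A value that is plausible for erythema above 0 need not fit ulceration, or any sign above 1. This stands; the range is illustrative.
- **No inference is at stake.** SAP Section 9.2 makes safety descriptive, and the randomized vehicle arm shows the background, balanced on average. This stands. The effect is attenuation, with no built-in advantage to one arm.
- **Partly covered already.** SAP Section 7.4 summarises baseline safety parameters by group, Listings 16.2.9.1 and 16.2.9.2 give individual values, and the table shells are in a separate document and may change, so a Visit 2 column cannot be ruled out. This softens the point, but the SAP text sets no rule that separates pre-existing from new signs.
- **The vital-signs contrast is weak.** Mean change is natural for continuous measures, and the laboratory tables also use absolute limits. This is fair, although adverse events do follow a treatment-emergent rule.

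A reader might infer that the A-101 minus vehicle difference is in fact diluted, and that counting only grades above baseline would recover it. The documents do not support the first, because they give no baseline prevalence. The arithmetic does not support the second: at w = 0 both rules give the same difference.

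**Conclusion.** The point holds as a conditional weakness in descriptive safety reporting. The planned counts make no use of a pre-dose grade that is already collected, and the Visit 3 window as written leaves that grade out of the safety summaries. Any irritation that precedes dosing and persists is reported as a reaction.

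Under the assumed 5 to 25% prevalence and 60% against 10% induced rates, the vehicle rate reads 14.5 to 32.5% and the ratio falls from 6.00 to between 4.28 and 2.15. This rests on equal prevalence in the arms, persistence to the visit tabulated, and independence of induced reactions from baseline status. At zero prevalence the effect is nil.

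A baseline-referenced count corrects the inflated arm rates and the ratio. It restores the risk difference only where reactions exceed the subject's own baseline grade. Used alone it can undercount: at p0 = 25% and w = 0 it would report 45% on A-101 against an assumed 60%, the less cautious error for tolerability. The change is a cheap improvement worth making, and no planned test or efficacy conclusion depends on it.

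**What to change.** In SAP Section 8.5 and the table list:

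1. Keep the frequency tables (14.3.5.1 and 14.3.5.2) and the raw above-0 and above-1 tables (14.3.5.3 to 14.3.5.6).
2. Add beside them, by sign or symptom, visit and arm, the number and percentage of subjects whose grade exceeds that wart's own Visit 2 pre-application grade. A shift table from Visit 2 would also serve.
3. Print the Visit 2 pre-application distribution by arm as a baseline row.
4. Reconcile the Visit 3 limit in SAP Section 8 with this, since as written it leaves out the Visit 2 grades.
5. Label each row as pre- or post-application, because the present titles do not say which grade is used.

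The cost is SAP wording, programming and a few extra tables; no new data are needed. The added count misses drug reactions that do not exceed a subject's baseline grade, which is why the raw counts must stay beside it.
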